5.7.3 Safety Analysis

Clinical AEs will be monitored throughout the study. All SAEs will be reported to the IRB in accordance with IRB policies. AEs that are not serious will be summarized in narrative or other format and submitted to the IRB at the time of continuing review. Since the study procedures are not greater than minimal risk, AEs are not expected. See section 6.2 on page 22 for further details.

5.8 Sample Size

This study will enroll up to 150 participants (see section 3.3.1 for details in enrollment timeline).

5.9 Interim Analysis

No interim efficacy analyses or corresponding stopping rules are proposed. Interim safety analyses will consist of ongoing reviews of AEs (if any) and will result in stopping the study only if life-threatening or serious diseases are found to be caused by the study, which is not anticipated.

6 SAFETY MANAGEMENT & REPORTING

6.1 Clinical Adverse Events

Clinical (AEs) will be monitored throughout the study. Since the study procedures are not greater than minimal risk, AEs are not expected. If any unanticipated problems related to the research involving risks to subjects or others happen during the course of this study (including SAEs) they will be reported to the IRB. As with any computer video game, seizure is a rare risk and possible SAE. However, subjects are required to have played video games in the past and a history of seizures excludes participants from taking part in this study.

6.2 Adverse Event Reporting

If, at any time, during any BioStream Training session or play of the alternate game session, the parent/guardian or teacher or therapist (as applicable) observes the subject displaying seizure symptoms, or becoming agitated, frustrated, disturbed, or in any other manner being negatively impacted (including in a manner that may pose a risk to the subject's safety or well-being or the safety or well-being of others) or in their judgment, believes the subject will or may become negatively impacted in any way (including in a way that may pose a risk to the subject's safety or well-being or the safety or well-being of others), they will immediately discontinue the session, stop the subject from engaging in any further sessions, and contact the Principal Investigator to inform him or her of this occurrence. AEs that are not serious but that are notable and could involve risks to subjects will be summarized in narrative or other format and submitted to the IRB at the time of continuing review.

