| Safety Evaluations | 
Subjects will always be supervised by a parent, teacher, or therapist (therapist includes Registered Behavior Technicians, assistant speech pathologists, assistant behavior analysts (BCABA), and teaching assistants) during use of the BioStream training and alternative game. Clinical adverse events (AEs) will be monitored throughout the study through parent reporting in the case of at home use and through teacher reporting in the case of in school use. Since the study procedures are not greater than minimal risk, AEs are not expected.
 |
| Statistical And Analytic Plan | 
Paired-sample t-tests will be used to measure changes from baseline within each group, and independent sample t-tests will be used to measure changes from baseline relative to the alternate game group for all endpoints.
 |

For all endpoints, we will determine whether there were observable changes in scores from baseline or relative to the alternate game group and whether these changes are statistically significant. Significance will be set at $p < 0.05$. Multiplicity of primary endpoints will be managed via statistical corrections.

**DATA AND SAFETY
MONITORING PLAN**

The PI will periodically review the data collection and storage practices associated with this study and determine whether changes to enhance confidentiality and privacy are required. The PI will frequently monitor the quality control of the data with staff and research assistants.

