3.3 Study Duration, Enrollment and Number of Sites

3.3.1 Duration of Study Participation

Enrollment for this study will last 18 months (starting on August 7, 2018 and ending on February 7, 2020). When a subject is enrolled, their first home visit will be within four weeks of their enrollment. Each phase lasts four weeks, but it is possible there will be delays of up to four weeks between phases for some participants. Therefore, for each subject, we expect to have all of our data for both phases 16 weeks from the date of enrollment at the latest. We expect the study to be complete by the beginning of February of 2020 at the latest.

Expected time commitment for parents and subjects for each phase can be found in tables 1 and 2 on pages 4-6.

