4.2 In-Person Study Visits

During the in-person study visits, parents and subjects will complete the following assessments, described in section 1.4 unless otherwise noted. Tables 1 and 2 also show details on the schedule of all in-person assessments for both phases.

Social Responsiveness Scale – Parent (SRS) – 10 minutes, parent only (may be administered by phone).

Childhood Joint Attention Rating Scale (C-JARS) – 10 minutes, parent only (may be administered by phone).

Dyadic Interaction Task – 10 minutes, subject only.

Eye Tracking Video Assessment – 10 minutes, subject only.

Ekman 60 Faces Test – 10 minutes, subject only.

Emotional Expression Video Assessment – 10 minutes, subject only.

Test of Variables of Attention (TOVA) – 22 minutes, subject only.

An introduction to game and equipment (Only Phase I Visit 1) – 40 – 60 minutes, with the parent/guardian, teacher, or therapist.

Subject Interview/Survey (described in section 5.4.1) – 10 minutes, subject only.

Parent/Teacher/Therapist Interview/Survey (described in section 5.4.2) – 10 minutes, parent, teacher, or therapist only.

Video Recording of Study Visits: All study team member visits to the home, school, or therapy center may be video recorded using a single or multiple video cameras and tripods.

Please note that for subjects who are using the BioStream Training in their school, therapy center or research organization, their parent/guardian only needs to be present for the first visit. After that visit, surveys involving the parent including the Social Responsiveness Scale and Childhood Joint Attention Rating Scale can be conducted over the phone.

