5.1.4 Video Game Interview Form (Parent-Report)

Parents or teachers or therapists will complete a weekly survey on the laptop provided by the Sponsor. The survey will ask questions concerning the subject's enjoyment and progress with the training as well as administration in the home or school environment. Survey is fully described in section 5.4.2.

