7.4.2 Risk Assessment

Use of BioStream Training or Alternate Game: The tasks associated with use of the BioStream Training or alternate game can produce feelings of frustration, anxiety, stress and fatigue including eye fatigue. These risks are no greater than those associated with minimal risk studies. As with any computer video game, seizure is a rare risk and possible SAE.

However, subjects are required to have played video games in the past and a history of seizures excludes participants from taking part in this study.

Psychological Stress and Anxiety: Due to the length of time associated with the assessments, some participants may experience fatigue, anxiety, or stress. Participants will be allowed to take breaks and stop at any time. Additionally, the presentation of unpleasant stimuli (including social interactions that are challenging for some youth with ASD) might be distressing to some participants. To minimize risk associated with the presentation of unpleasant stimuli, several precautions will be taken: (i) only members of the study team that are trained to conduct study visits by a Board Certified Behavior Analyst with experience in working with children with ASD, will conduct study visits, (ii) Parents/guardians will be shown examples of stimuli as part of the consent process and will be asked whether they feel confident that their child will not find these overly distressing, (iii) the parent/guardian or teacher or therapist (as applicable) will be instructed and agree to oversee gameplay to look for signs of distress in the subject and the tasks will be stopped if the subject appears distressed or requests to stop.

Risks Associated with Behavioral Data Collection: These risks are no greater than those associated with minimal risk studies.

Breach of Confidentiality: Confidentiality is carefully guarded to address issues of privacy and insurability. In particular, each subject is assigned a unique alphanumeric identifier immediately upon recruitment. Although a list linking the study number to the subject's name is maintained for future studies and contact, the name does not appear on any other document (other than Informed Consent Forms and Assent Forms). The families are informed of this link and are assured that only the PI has access to that list. The purpose of the list linking study ID number to the name is to record who we have already recruited so that we accidentally do not re-approach any family.

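### AE monitoring is promised for the whole study, but the only defined capture procedure covers game sessions, so events outside them are likely to be under-ascertained

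*Combined protocol and SAP*

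**What the plan says.** - **Scope of monitoring.** The Synopsis (Safety Evaluations), 5.7.3 and 6.1 each promise AE monitoring over the whole study. The Synopsis says this works "through parent reporting in the case of at home use and through teacher reporting in the case of in school use". It names no reporter for therapy-center or research-organization use.
- **Capture procedure.** Section 6.2 begins "If, at any time, during any BioStream Training session or play of the alternate game session" and applies when "the parent/guardian or teacher or therapist (as applicable) observes the subject displaying seizure symptoms" or sees, or foresees, some other negative effect. That adult ends the session, stops further sessions and contacts the PI. Therapists are included here, unlike in the Synopsis.
- **Onward reporting.** Sections 5.7.3 and 6.1 send serious AEs and unanticipated problems to the IRB. Section 6.2 adds that "AEs that are not serious but that are notable and could involve risks to subjects will be summarized in narrative or other format" for continuing review. None of these duties is limited to sessions. Section 5.9 adds ongoing review of AEs.
- **Expected harms.** Section 7.4.2 states: "Due to the length of time associated with the assessments, some participants may experience fatigue, anxiety, or stress". The response is breaks and stopping; no recording step follows. It also lists eye fatigue from play.
- **Regular contacts.** The weekly survey (5.1.4) covers "enjoyment and progress with the training as well as administration in the home or school environment". The visit interviews (5.4.1, 5.4.2) are described in terms of enjoyment and feedback.
- **Parents.** For children who play at a school, center or research organization, "their parent/guardian only needs to be present for the first visit" (4.2). Later SRS and C-JARS contacts may be by phone.
- **Gap.** Section 3.3.1 says "it is possible there will be delays of up to four weeks between phases for some participants". In the Synopsis, the first Phase II visit follows a week of play.

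**The concern.** An IRB duty governs what happens once the team knows of an event. The weakness lies before that step: outside game sessions, no form, question or time window is given by which the team would come to know. The data and safety monitoring plan (7.4.1) does not fill the gap, since it covers confidentiality and data quality and does not mention AEs.

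What is at stake is how a safety result would be read. The protocol expects no AEs. If collection depends on unprompted reports from whoever supervises play, a count near zero could reflect either few events or little asking, and the data could not tell the two apart. The ongoing review in 5.9 can act only on what has been collected. The planned output for non-serious events is a narrative to the IRB, with no count by assigned game.

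**Working it through.** No sample-size, power or event figure is involved, so the main check sets the sections side by side.

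| When an event occurs | Who could notice it | Stated step to the PI | Stated duty once known |
|---|---|---|---|
| During a game session | Parent, teacher or therapist (6.2) | Yes (6.2) | IRB reporting (5.7.3, 6.1, 6.2) |
| During an assessment visit | Trained study team member (7.4.2) | None written | Same |
| After a session | Parent, or no one named | None written | Same |
| Between phases | Parent, or no one named | None written | Same |

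The last column is filled in every row. The third is filled only in the first. The gap is therefore in capture, not in onward reporting.

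**Could an existing contact fill the third column?** The weekly survey, the visit interviews and the parent SRS/C-JARS contact all take place, but none is described as asking about AEs. The schedule lists no contact between the last Phase I visit and the first week of Phase II play. A seizure in that interval would be reportable if known, and seizure history is an exclusion (3.4.2), but no listed contact would bring it to light before play resumes.

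**Context on time, from the protocol's own tables**

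1. Play per phase: 20 × 20 min = 400 min = 6.67 h; 20 × 100 min = 2,000 min = 33.33 h. Both match the protocol.
2. Phase I testing (Table 2): PPVT 20 + Visit 1 Ekman 10 + dyadic 50 + eye tracking 50 + Ekman 50 + emotional video 50 + TOVA 109 = 339 min = 5.65 h.
3. Testing share, Phase I: 5.65/(5.65 + 6.67) = 46%; 5.65/(5.65 + 33.33) = 14%.
4. Phase II testing (Table 3): 4 × 40 + 87 = 247 min = 4.12 h. Both phases: 339 + 247 = 586 min = 9.77 h, against 13.33 to 66.67 h of play, a share of 42% to 13%.
5. Adding consent/assent (30 min) and the subject interview (40 min) to Phase I gives 409 min = 6.82 h, and the share becomes 51% to 17%. The figure thus depends on which rows are counted.
6. Share of the calendar: 28 × 24 = 672 h; 6.67/672 = 1.0%; 33.33/672 = 5.0%.

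Separately, the rows in step 5 reproduce Table 2's lower subject total (409 + 400 = 809 min = 13.48 h). At the upper end they give 409 + 2,000 = 2,409 min = 40.15 h, where the table prints 41.15 h. This does not affect the present point.

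**The case against.** The other side has a good case on several points.

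- **A reader might infer that events outside sessions have no reporting route at all.** The documents do not support that. Serious AEs, unanticipated problems and notable non-serious AEs go to the IRB whenever they occur. A seizure, which 6.1 calls a possible serious AE, would be reportable at any time.
- **Assessments are not unobserved.** Trained study team members conduct the visits, and the child may pause or stop. What is missing is a recording step, not an observer.
- **Parents of in-school children are not out of reach.** They complete the SRS and C-JARS at five Phase I and four Phase II visits, by phone if need be, and subjects may contact the team with questions (1.2).
- **The contacts may ask more than is described.** Sections 5.4.1 and 5.4.2 use open-ended wording, 5.4.2 allows observational information, and 1.2 lets weekly-survey data serve study monitoring. The forms are not in the documents. This limits the point to what the protocol commits to.
- **A reader might infer that AE counts will be biased between arms.** That is not shown. Section 6.2 treats both games alike, 3.1.4 makes the visits otherwise the same, and assignment is random. Blinding is stated only for the video annotators, so differential reporting is possible, but nothing establishes it.
- **A reader might take the time shares as the share of harm missed.** They are not. Testing time is spent with study staff, and the 672 hours include sleep.

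What remains is that a whole-study promise has a written capture method for sessions only. Calling the study minimal risk lowers the stakes but does not supply the method.

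**Conclusion.** The point holds as a gap in ascertainment. Under-ascertainment is likely, but its size cannot be estimated: the documents give no event rate and no survey forms. It would be too strong to say that few or no AEs will be recorded whatever the true rate, because the trigger in 6.2 is broad during play and the general duties apply throughout.

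The conclusion assumes that the surveys and interviews contain no AE item beyond what the protocol describes. If the actual forms do ask about AEs, the remaining defect is that the protocol does not say so and gives no collection window. The Synopsis and 6.2 also disagree on who reports in therapy centers, and that needs reconciling in either case. This should be corrected, but it does not undermine the efficacy analysis.

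**What to change.** 1. State an AE collection window from Phase I Visit 1 to the last visit, including any gap between phases.
2. Write one short, fixed AE question set, worded identically in both arms and covering the risks named in 7.4.2. Add it to the weekly survey, the visit interview and the parent SRS/C-JARS contact, and ask it once at the contact that starts Phase II. The schedule does not list that contact, so it needs to be named; a phone call would do.
3. Give study staff a place to record events seen during assessments.
4. Tabulate AEs by assigned game, with denominators, as well as in narrative.
5. Reconcile the Synopsis, 5.7.3, 6.1, 6.2 and 7.4.2, and name a reporter for every setting. Keep AE reporting separate from the session-stopping rule in 6.2; no change to that rule is proposed.

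**Cost:** a few questions on existing forms and calls, possibly one brief call per child, and one table. Solicited questions will raise reported AE counts in both arms, which should be said when results are presented.

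The planned enrollment window closed in February 2020 and the SAP supplement is dated April 2022. If data collection has ended, only items 4 and 5 remain open, and the report should state how AEs were ascertained and refrain from treating a low count as evidence of safety.

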4.3.1 Early Termination Study Visit

Subject Exit Interview/Survey

In the case that a subject decides to leave the study early, the subject will be asked to complete a final interview. This interview will discuss the reasons for leaving the study, will be completely voluntary, and may be discontinued at any time during the interview by the subject.

Parent Exit Interview/Survey

In the case that a subject decides to leave the study early, the parent/guardian will also be asked to complete a final interview. This interview will discuss the reasons for the subject leaving the study, will be completely voluntary, and may be discontinued at any time during the interview by parent/guardian.

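### Sections 6.2, 7.4.2 and 4.3 do not give one instruction for stopping a child's game sessions, and the plan does not say whether a stopped child is still assessed and analysed

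*Combined protocol and SAP*

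**What the plan says.** Section 6.2 (Adverse Event Reporting) addresses the parent, teacher or therapist who supervises play of either game. The trigger is that this adult "observes the subject displaying seizure symptoms, or becoming agitated, frustrated, disturbed, or in any other manner being negatively impacted". It is also enough that the adult "believes the subject will or may become negatively impacted in any way". The consequence is that "they will immediately discontinue the session, stop the subject from engaging in any further sessions", and that they inform the PI. No severity or duration threshold is given, and no step for review or resumption.

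Section 7.4.2 (Risk Assessment) says that the tasks of both games "can produce feelings of frustration, anxiety, stress and fatigue including eye fatigue", and adds: "These risks are no greater than those associated with minimal risk studies". A separate paragraph on psychological stress lists precautions against unpleasant stimuli. One of them concerns gameplay overseen by the same adult: "the tasks will be stopped if the subject appears distressed or requests to stop". It says nothing about later sessions.

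Section 4.3 lists safety among the reasons for discontinuing a child from the study, at the PI's discretion. Section 4.3.1 covers a subject who decides to leave early; in that case "the subject will be asked to complete a final interview".

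Section 5.7.2 restricts the primary analysis to randomized subjects with both initial and final visit data. Section 1.3 allows up to 20 sessions per phase, and section 5.8 up to 150 participants.

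**The concern.** Frustration is named in 7.4.2 as something the games can be expected to cause, and in 6.2 as a reason to end all further play. A supervisor who follows 6.2 to the letter stops training at the first sign of it. A supervisor who works from 7.4.2 stops the task and has no instruction about the next day. With 10 sites and with parents, teachers and therapists all supervising, the rule applied could vary from child to child.

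Two things are at stake statistically. The first is exposure, since children stopped early receive less of the assigned game. The second is selection. If a stopped child has no final visit, that child leaves the primary analysis, and the reason for leaving is the child's reaction to the assigned game. The decision rests on the adult's judgement. Section 3.2 has blinding in its heading but describes none for that adult; the documents state blinding only for those who annotate the dyadic-task videos.

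**Working it through.** **Step 1: the three instructions side by side.**

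| | 6.2 | 7.4.2 | 4.3 |
|---|---|---|---|
| Trigger | Seizure symptoms, agitation, frustration, or any actual or possible negative impact | Child appears distressed or asks to stop | Safety reasons |
| Who decides | Supervising adult, who then informs the PI | Not stated; the adult oversees play | PI |
| Consequence | Session ended, further sessions stopped | Tasks stopped | Discontinued from the study |
| Later sessions | None; no route back described | Not addressed | Not addressed separately |

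A visibly distressed child falls under both 6.2 and 7.4.2, and the two state different consequences. A child who is frustrated but not distressed falls under 6.2 only, although 7.4.2 calls that effect minimal risk.

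**Step 2: how many children 6.2 could stop.** The documents state no rate of frustration, no dropout rate and no expected number of stops, so there is no plan figure to reproduce. Sessions: k = 20 (section 1.3, the maximum for one phase). Children: 150 (section 5.8, the maximum). The per-session trigger rate p is assumed.

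With independent sessions, the share with at least one trigger is 1 − (1 − p)^20:
- p = 1%: 1 − 0.99^20 = 0.182
- p = 2%: 1 − 0.98^20 = 0.332
- p = 5%: 1 − 0.95^20 = 0.642

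Sessions of the same child are unlikely to be independent. With a beta-binomial model and assumed within-child correlation ρ, set s = 1/ρ − 1, a = p·s and b = (1 − p)·s. The share is then 1 − B(a, b + 20)/B(a, b), where B is the beta function. For ρ = 0.3, s = 2.333; for ρ = 0.1, s = 9.

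| Assumed p | Independent | ρ = 0.1 | ρ = 0.3 |
|---|---|---|---|
| 1% | 18.2% (27 of 150) | 10.3% | 5.6% (8 of 150) |
| 2% | 33.2% (50) | 19.7% | 10.9% (16) |
| 5% | 64.2% (96) | 42.5% | 25.3% (38) |

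A child who plays both phases has up to 40 sessions. At p = 1%, 2% and 5% the shares are then 33.1%, 55.4% and 87.1% with independence, and 7.0%, 13.6% and 30.7% with ρ = 0.3.

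**Step 3: what happens to a stopped child's data.** No section says whether the assessment visits continue after a 6.2 stop. If they do, the child stays in the 5.7.2 analysis set with reduced exposure. If they do not, the child drops out of it. The endpoint is tied to the assessment after the last game session, so it is also unclear which visit counts as final for a child stopped early. The Supplement to the SAP adds mixed ANOVAs of pre and post scores and does not address this.

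As an illustration only, suppose p were 1% in one arm and 2% in the other. The stop rates would differ by 33.2 − 18.2 = 15.0 percentage points with independence, or 10.9 − 5.6 = 5.3 points with ρ = 0.3.

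**The case against.** Several points on the other side are sound.

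- **The passages can be followed together.** The 7.4.2 stop is triggered by apparent distress, in a different paragraph from the one that mentions frustration, and it does not say that play may resume. A supervisor could stop the task, hold further sessions and call the PI. This stands, and it narrows the conflict to a missing threshold, a missing decision step and an unclear decision-maker.
- **A reader might infer a permanent bar.** The text does not use that word. Contact with the PI, together with the PI's discretion in 4.3, could mean a hold until the PI decides. No such review is written, so the text settles neither reading.
- **A reader might infer that stopped children get only an exit interview.** Section 4.3.1 applies when a subject decides to leave. A child stopped by an adult has not done so, and no passage cancels that child's visits. The plan is silent on the matter.
- **A reader might infer that stops will differ by arm.** The comparator is described first as a modified version of the training without the same exercises, with an E-rated game as an alternative. The documents give no evidence of different stop rates. Difference by arm is a possibility that the plan leaves open.
- **The completer restriction is a weakness whatever 6.2 says.** True, but 6.2 adds a reason for missing data that is linked to the child's reaction to the assigned game.

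**Conclusion.** The concern holds as an inconsistency with a possible effect on the analysis. Section 6.2 is broader in its trigger and heavier in its consequence than 7.4.2, and it places the first decision with a different person from 4.3. The plan does not say what becomes of a stopped child's outcome data.

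The size is unknown. A reader might conclude that a large share of children will be removed from training, but that rests on an assumed rate and on independent sessions. At assumed rates of 1% to 5% per session over the full 20 sessions, the share stopped runs from about 6% to 64%, depending mostly on how far triggers cluster within children. These shares count children whose training would stop under a literal reading. They become losses to the primary analysis only if the final visit is also missed. The inconsistency itself does not depend on any rate.

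**What to change.** Reconcile 6.2, 7.4.2 and 4.3 so that one instruction applies. Its content, including any threshold, review or resumption step, is for the investigators and the IRB.

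Whichever instruction is kept, state in 4.3 and 5.7.2 that a stop of game sessions is not by itself withdrawal from the study. Unless the family declines or the PI discontinues the child from the study, the already scheduled outcome assessments are still sought, and the child is analysed in the assigned arm. Name the visit that counts as final for such a child. This leaves the stopping rule and the PI's safety discretion untouched.

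The cost is protocol wording, since the visits are already scheduled. Some stopped children will decline the remaining visits, so the change reduces the selection but does not remove it.
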